## 9.5 Outcomes

All oral rinse products are commercially available, low risk products. Therefore, adverse outcomes are anticipated to be extremely rare, and will be reviewed weekly by the study team/committee. Any adverse event will be documented in our CDART database system.

The qRT-PCR assay for our primary outcome will be documented in an excel spreadsheet generated by the qRT-PCR assay quantification device, available weeks to months after sample collection when the experiments are conducted. If qRT-PCR proves unsuccessful, antigen-based assays will be used instead to quantify viral protein antigen level (Spike or N protein) using a sandwich ELISA or rapid antigen assays. These outcomes will be documented in excel spreadsheets generated by study personnel, available weeks to months after sample collection when the experiments are conducted. Samples will be run in large batches to limit batch effects.

The viral infectivity assay for our tertiary outcome will be documented in an excel spreadsheet generated by the viral infectivity assay quantification device, available weeks to months after sample collection when the experiments are conducted. Survey results will also yield excel spreadsheets of data, available shortly after data collection completion.

The outcomes do not include patient treatment response, and therefore the outcomes will not be reviewed and adjudicated by an outside committee. The study personnel will constitute their own committee that meets weekly, and they will review and evaluate the data once these experiments are conducted. The committee will not be masked to the participant's group assignment; the statistician will conduct analyses and then the committee will evaluate the data to reach scientific conclusions on which mouthrinse is more effective.

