### **Objectives**

The primary objectives are to quantify the impact of antiseptic mouthwashes on salivary protein antigen levels and viral RNA of the SARS-CoV-2 virus in COVID-19+ patients. The tertiary objectives are to quantify the impact of antiseptic mouthwashes on salivary viral infectivity in COVID+ patients, and to determine patients' acceptance of using antiseptic mouthwashes in healthcare settings.

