## 1. STUDY OBJECTIVES

### 1.1 Primary Objectives

The primary objectives of this study are to determine the efficacy of antiseptic mouthwashes on reducing SARS-CoV-2 viral RNA and protein antigen levels in COVID+ patient saliva. *We hypothesize that COVID-19+ patients will have a >95% reduction in SARS-CoV-2 viral RNA and protein antigen levels following a 60 second oral rinse with an antiseptic mouthrinse and that this reduction will persist for at least 30 minutes.* These primary objectives will assess SARS-CoV-2 viral load based on viral RNA measured by quantitative real time PCR and viral protein antigen levels measured by rapid antigen or sandwich ELISA assays. These objectives provides urgently needed data to guide healthcare workers on the proper use of specific commercially available mouthwashes capable of reducing SARS-CoV-2 in saliva and potentially limiting COVID-19+ transmission.

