#### **Primary Outcomes**

The analyses will compare viral RNA level (qRT-PCR) and protein antigen level (sandwich ELISA or rapid antigen) of SARS-CoV-2 between mouth rinse types and across the time course.

Data generated from the qRT-PCR and sandwich ELISA or rapid antigen assays will be presented as mean standard deviation for normally distributed data and as median [Interquartile range] for

non-normally distributed data. P values will be reported as two tailed. Between group comparisons will be performed using a Student's t test or Mann-Whitney U test. Normality will be assessed using the Kolmogorov-Smirnov test, and logistic regression will be performed with robust standard errors.

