### 9.5.1 Primary Outcomes

The primary objectives of this study are to determine the efficacy of antiseptic mouthwashes on reducing SARS-CoV-2 viral RNA and protein antigen levels in COVID+ patient saliva. *We hypothesize that COVID-19+ patients will have a >95% reduction in SARS-CoV-2 viral RNA and protein antigen levels following a 60 second oral rinse with an antiseptic mouthrinse and that this reduction will persist for at least 30 minutes.* These primary objectives will assess SARS-CoV-2 viral load based on viral RNA measured by quantitative real time PCR and viral protein antigen levels measured by rapid antigen or sandwich ELISA assays. These objectives provides urgently needed data to guide healthcare workers on the proper use of specific commercially available

mouthwashes capable of reducing SARS-CoV-2 in saliva and potentially limiting COVID-19+ transmission.

Outcome assessments will be conducted weeks to months after the study visit, when qRT-PCR and sandwich ELISA or rapid antigen assays are conducted in the COVID core and the [name] lab.

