## 9.6 Data Analyses

qRT-PCR and sandwich ELISA or rapid antigen: Data will be presented as mean standard deviation for normally distributed data and as median [Interquartile range] for non-normally distributed data. P values will be reported as two tailed. Between group comparisons will be performed using a Students t test or Mann-Whitney test. Normality will be assessed using the Kolmogorov-Smirnov test, and logistic regression will be performed with robust standard errors. Methods adapted from Bullard *et al* 2020.

Viral infectivity: The viral infectivity analysis will compare infectivity levels between mouth rinse types and across the time course for calculation of the reduction factor (RF). The RF will be calculated as the difference in the quotient of the infection titre before ('control titration') and after

the mouthrinse ('remaining virus'). Therefore, the log10 titre and its (double) standard deviation (SD) were calculated as well as the variance of the RF.

Survey results will be evaluated using bivariate, descriptive statistics and non-parametric methods as appropriate for the question type.

Power Calculation: Based on similar viral infectivity studies evaluating mouth rinse efficacy against other enveloped viruses, we used power calculations to estimate effect size and determine sample size as a function of length of mouthrinse time course. The sample size is justified by a paired t-test on outcomes between time points. With ten simultaneous comparisons (T1-T0, T2-T1, T2-T0, T3-T0, T3-T2, T3-T1, T4-T3, T4-T2, T4-T1, T4-T0) = 60 minute time course, the sample size n=78 can detect the effect size in Cohen's d =0.7, which is between medium and large, under 80% power and 0.016 type-I error rate by Bonferroni correction. Analyses will compare viral RNA level (qRT-PCR), protein level (sandwich ELISA and rapid antigen) or viral infectivity levels between mouth rinse types and across the time course. ANCOVA models will be utilized to look at changes in viral load and infectivity logarithmically before and after treatment.

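### The plan gives two incompatible rules for the primary outcome (RNA and antigen both primary, or antigen only as a substitute for qRT-PCR), leaves the switch between them undefined, and allocates no alpha across them

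*Combined protocol and SAP*

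**What the plan says.** Four places treat the two measures as joint primaries.

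- Précis, Objectives: "The primary objectives are to quantify the impact of antiseptic mouthwashes on salivary protein antigen levels and viral RNA of the SARS-CoV-2 virus".
- Section 1.1 sets out to determine the "efficacy of antiseptic mouthwashes on reducing SARS-CoV-2 viral RNA and protein antigen levels in COVID+ patient saliva".
- Section 9.1, Primary Outcomes: "The analyses will compare viral RNA level (qRT-PCR) and protein antigen level (sandwich ELISA or rapid antigen) of SARS-CoV-2 between mouth rinse types".
- Section 9.5.1: "The primary objectives of this study are to determine the efficacy of antiseptic mouthwashes on reducing SARS-CoV-2 viral RNA and protein antigen levels".

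Section 9.5 differs. It speaks of the primary outcome in the singular, assigns it to qRT-PCR, and continues: "If qRT-PCR proves unsuccessful, antigen-based assays will be used instead to quantify viral protein antigen level". The antigen may be Spike or N, and the platform sandwich ELISA or a rapid test. The platform wording also varies: "protein antigen level (sandwich ELISA or rapid antigen" in section 9.1, but "protein level (sandwich ELISA and rapid antigen" in section 9.6.

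Section 9.5 also says that study personnel form their own committee, which evaluates the data once the statistician has run the analyses: "The committee will not be masked to" participants' group assignment.

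Section 10.3.3 plans triplicate runs with positive and negative controls for qRT-PCR, infectivity and antigen assays. The only error rate given anywhere is 0.016, tied in sections 2.2, 9.1, 9.2 and 9.6 to comparisons between time points.

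**The concern.** An outcome cannot be primary in its own right and also only a stand-in for another. Under the first rule antigen is always analysed and always counts. Under the second it counts only if qRT-PCR fails. The plan does not say which rule governs or, under the first, whether a rinse must succeed on both outcomes or on either.

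The switch is also unguarded. *Unsuccessful* could mean that the assay did not work or that it showed no effect, and the text does not exclude the second meaning. No one is named to decide, no deadline is set, and no masking is required. Section 3 prepares the same inactivated aliquots for RNA and antigen work, and section 9.5 puts the assays weeks to months after sampling. Antigen could therefore be run, or given prominence, once RNA results are known.

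Section 1.1 says that the results are meant to guide healthcare workers on specific rinses. A reader of the final report needs to know which outcome was meant to carry that claim, and at what error rate.

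**Working it through.** **Text comparison**

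| Question | Précis, 1.1, 9.1, 9.5.1 | 9.5 |
|---|---|---|
| How many primary outcomes? | Two | One |
| Is antigen analysed if qRT-PCR works? | Yes | Not as written |
| Are both needed, or either? | Not stated | Not applicable |
| Alpha across the two outcomes | Not stated | Not stated |
| What counts as qRT-PCR failure? | Not applicable | Not defined |

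Section 10.3.3 lists antigen assays among those run on all samples. That fits the first rule, not the second.

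**Size of the consequence.** The plan gives no figure to reproduce here, so what follows is an illustration.

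Inputs:
- Two-sided tests (section 9.6).
- α = 0.016, the plan's only level, and α = 0.05, an assumed conventional level. The critical values are 2.409 and 1.960.
- Five rinses against one saline arm, 80 per arm (section 3).
- The RNA–antigen correlation is not in the documents. The range 0 to 0.8 is assumed.
- One contrast per rinse and outcome, with no true effect.

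*One rinse, either outcome suffices.* P(either) = 2α − P(both).
- Correlation 0: 1 − (1 − α)². At 0.05, 1 − 0.95² = 0.0975. At 0.016, 1 − 0.984² = 0.0317.
- Correlation 0.8 (bivariate normal): at 0.05, 0.100 − 0.022 = 0.078. At 0.016, 0.032 − 0.006 = 0.026.

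*Five rinses.* For each outcome, z = (rinse mean − saline mean)/√2 in standardised units, so contrasts share the saline arm. The event is any |z| above the critical value. Results are by simulation with a normal approximation.

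| Level | Per rinse, one outcome | Per rinse, either | Five rinses, one outcome | Five rinses, either |
|---|---|---|---|---|
| 0.016 | 1.6% | 2.6%–3.2% | 6.5% | 10%–13% |
| 0.05 | 5% | 7.8%–9.75% | 18% | 27%–33% |

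The lower figure in each range is for correlation 0.8, the upper for 0.

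*Both outcomes required.* P(both) at 0.05 is 0.05² = 0.25% at correlation 0 and 2.2% at 0.8, so the error is below nominal.

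*Open antigen choices.* RNA plus Spike or N by either platform makes five measures. If all were available and independent, the chance of at least one false positive per rinse would be 1 − 0.95⁵ = 22.6%, or 1 − 0.984⁵ = 7.75% at 0.016. Positive correlation lowers both.

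**Does fixing the rule need more patients?** At the plan's effect size (d = 0.7, 80% power), splitting 0.016 into 0.008 per outcome needs 29 for a paired t-test or 52 per arm for a two-sample t-test. The plan has 80 per rinse. If both outcomes are required at 0.016, two-sample power is 0.973 per outcome at 78 per arm, so joint power is at least 1 − 2 × 0.027 = 0.946.

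**The case against.** The best defence is that *unsuccessful* means technical failure. The sentence sits in a paragraph about how assay output is recorded, and section 10.3.3 already plans positive and negative controls and quality checks by laboratory staff. A switch made on those grounds, without sight of arm-level results, would not inflate the error rate. This reading is plausible and narrows the gap. It does not close it, because section 9.5 does not link the trigger to those controls and sets no time for the decision.

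A reader might infer that the unmasked committee will pick the primary outcome after seeing which assay favours a rinse. The documents do not support that. Section 9.5 asks the committee only to judge which rinse is more effective after the statistician's analyses, and no section gives it the qRT-PCR-to-antigen decision. The lack of masking is an aggravating circumstance, not the mechanism.

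The error rates also depend on the adverse reading. Section 9.5.1 hypothesises a reduction in RNA and antigen together, and if both were required there would be no inflation. The level of 0.05 is assumed. Much of the five-rinse figure comes from testing five rinses (6.5% at 0.016, or 18% at 0.05, with one fixed outcome), which is a separate matter. These points limit the numbers but leave the contradiction in place.

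**Conclusion.** The contradiction is certain from the text: two primary-outcome rules, no statement of which governs, an undefined trigger, an open antigen target and platform, and no alpha allocation. That a choice could be made after results are seen is an open route, not a stated intention.

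The size depends on the reading. If either outcome suffices, the error is about 1.6 to 2 times nominal per rinse (2.6/1.6 and 3.2/1.6 at the plan's 0.016). If both are required, or if the switch is purely technical and blind to results, this source adds no inflation. The figures rest on assumed correlations, one contrast per rinse and, for the higher set, an assumed 0.05. The plan should be corrected before assay results are linked to arms.

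**What to change.** 1. State one rule, in the same words, in sections 1.1, 9.1, 9.5, 9.5.1 and 9.6, and align the Précis. Any of three would do: RNA first and antigen second in a fixed sequence; both primary with the alpha split; or both required for success.
2. Delete the substitution sentence in section 9.5. Otherwise limit it to failure of the positive or negative controls already planned in section 10.3.3, judged by laboratory staff without arm-level results and recorded before unblinding.
3. Name one antigen target and one antigen assay in advance, and remove the difference between sections 9.1 and 9.6. The documents give no ground for ranking one platform above the other, so that choice is the investigators'.

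The cost is wording, plus a slightly stricter alpha, a fixed testing order, or a small loss of power if both outcomes are required. At the plan's effect size none of these needs more than the planned 80 per rinse.

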### **Design and Outcomes**

Randomized, double-blind prospective trial to test the efficacy and acceptability of therapeutic, antiseptic mouth rinses to inactivate the SARS-CoV-2 virus, and to reduce protein antigen levels and viral RNA in saliva of COVID-19 positive patients aged 18-65 years old. All mouthrinses are commercially available and will be used according to on-label instructions. Patients will be randomized to a mouthrinse and will be asked to give a saliva sample immediately before and after a one minute mouthwash. Saliva samples will be collected from patients at 15 minute intervals thereafter up to an hour (15, 30, 45 and 60 minutes). The samples will be stored and used for qRT-PCR detection of viral SARS-CoV-2 RNA, sandwich ELISA or rapid antigen tests for detection of SARS-CoV-2 protein antigens, and viral infectivity assays. Patients will also complete a short-survey on the taste and experience of using the mouthwash. This study involves one, 75-90 minute visit.

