### **Sample Size and Population**

We will enroll 80 outpatient COVID+ subjects per mouth rinse, with 6 mouth rinses, requiring us to enroll 480 COVID+ patients. Patients will be randomized to their mouthrinse. These patients will have already had a confirmed COVID+ test prior to enrollment. There will be no stratification to our randomization. In addition to having a COVID+ test, patients will need to be at least 18 years of age and at most 65 years of age and in good oral health without any known allergies or reactions to commercial

dental products, mouthrinses or iodine. Patients who are pregnant, nursing/lactating, who have a cognitive or developmental disability, who are taking lithium, who have or have ever had a thyroid problem, who have kidney dysfunction, who have an active oral herpes flare up, who have any oral viral infection and/or flare up, who have significant mucosal tears, growths or damage to their mouth, who have uncontrolled severe periodontal disease with bleeding gums, and those who have xerostomia will be excluded from the study. There is no exclusion criteria based on gender or race.

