### **9.4 Interim Analyses and Stopping Rules**

An interim analysis will be conducted after 120 patients are enrolled and samples collected; block randomization will be planned to randomize in batches of 120 participants, with 20 randomized to each mouthrinse. Therefore, we can do an interim analysis with an  $n=120$ . This sample size is sufficient to determine antiviral efficacy at 30 minutes post-mouthrinse. If mouthrinses are ineffective at reducing viral infectivity at timepoints 15 and 30 minutes, then that mouth rinse arm will be discontinued for further enrollment and will be removed from the block randomization calendar, with initiation of a subsequent trial with fewer arms. This will allow us to enroll sufficient numbers of patients to statistically evaluate longer time point efficacy for the mouthrinses with antiviral efficacy (the longer time points require larger samples sizes for sufficient statistical power).

If no mouthrinse has antiviral effects at this interim analysis point, the study will be stopped due to lack of efficacy. Because all oral rinse products are commercially available, low risk products that have previously undergone extensive safety testing and approval procedures, we do not anticipate a situation where safety concerns to participants necessitates halting the study. Adverse events will be reported and reviewed by our internal quality control committee. Medical problems that occur in our facility will be reported as needed to the IRB board and emergency medical personnel will be contacted to care for the patient and potentially bring them to the adjacent UNC medical hospital. If a significant number of adverse events or reactions are witnessed (defined as more than 1 per every 20 patients), a safety review will be triggered and study personnel will look at the records in an unblinded fashion to see if one mouthrinse is causing reactions. If that is the case, the mouthrinse study arm associated with adverse events will

be discontinued, but the mouthrinse arms associated with minimal adverse events will continue.

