#### **10.3.2 Quality Control Committee**

The investigators and study coordinators will meet weekly as an internal quality control committee to review consent documents, CDART data forms, and unanticipated problems with recruitment or adverse events. There is only one site for this study. The use of on-label, widely used mouthrinses (like Listerine or Crest) and collection of saliva carry minimal risk for participants, apart from the very rare, undiagnosed allergy, which

would be managed through proper referral to the neighboring UNC hospital. Therefore, there is no study quality control committee.

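### The study team's own committee is declared unmasked, against the double-blind design, and nothing keeps results by arm away from it while enrolment continues

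*Combined protocol and SAP*

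**What the plan says.** The Précis (Design and Outcomes) describes a "Randomized, double-blind prospective trial", and Sections 3 and 9.1 repeat the double-blind label. Section 5.2 uses an opaque, unmarked syringe so that neither participants nor study personnel see the colour of the rinse. Sections 6.2.2, 6.2.3 and 9.2 blind the researcher who collects the saliva.

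Section 9.5 rules out an outside committee and continues: "The study personnel will constitute their own committee that meets weekly, and they will review and evaluate the data once these experiments are conducted". It then says "The committee will not be masked to" the participants' allocation. The statistician is to run the analyses, and the committee is to conclude which rinse works better.

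Section 9.4 says: "An interim analysis will be conducted after 120 patients are enrolled and samples collected". Arms judged ineffective at 15 and 30 minutes stop enrolling. Sections 7.1 and 7.6 state that there is no safety monitoring board.

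On who does what, Section 10.3.2 says "The investigators and study coordinators will meet weekly as an internal quality control committee", and Section 10.2 has study coordinators collecting, entering and managing participant data.

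**The concern.** The group that Section 5.2 blinds is the group that Section 9.5 unmasks. No section gives a date before which the committee stays masked, or says that visit or laboratory staff are kept off it.

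The primary outcomes are laboratory assays, which limits the scope for biased measurement but does not remove judgement. Several decisions rest with the team and have no fixed criterion:

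- whether PCR has failed, so that antigen assays replace it (Section 9.5)
- whether an arm is ineffective at the interim (Section 9.4)
- whether a participant is withdrawn at the investigator's discretion (Sections 6.2.5 and 8)
- whether an assay run passes its quality checks (Section 10.3.3); masking of laboratory staff is stated nowhere

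If the people deciding know how each arm is doing, these choices can lean towards or against an arm without anyone intending it.

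**Working it through.** **Inputs**

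- Planned total (Précis, Sample Size and Population): six rinses with 80 participants each, "requiring us to enroll 480 COVID+ patients".
- Interim point (Section 9.4): the plan is to "randomize in batches of 120 participants, with 20 randomized to each mouthrinse", with the interim after the first batch.

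**Plan's own figures**

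- Total: 6 × 80 = 480, as stated.
- Interim: 6 × 20 = 120, as stated.

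**Participants enrolled after the interim**

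- All six arms continue: 480 - 120 = 360, and 360/480 = 75%. This is the maximum.
- Each retained arm has 80 - 20 = 60 left to enrol. With 5, 4, 3, 2 or 1 arms kept, 300, 240, 180, 120 or 60 remain.

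**Does unmasking the first batch reveal later assignments?**

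- Once a batch is complete with 20 per arm, it carries no information about the order of the next. With six arms, a guess at the next participant's rinse is right with probability 1/6 = 16.7%, which is chance.
- The answer differs only if assignments became known while a batch was still running. I simulated this with 5,000 replicates, assuming each batch is one random permutation with 20 per arm (Section 9.4 gives the batch but no smaller block size). The best guess is then right about 24% of the time with six arms, and about 42% against 33% by chance with three. On average about one assignment per batch becomes certain. No section says that this will happen.

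**Who sees results by arm at the interim?**

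- Dropping an arm requires results by arm (Section 9.4).
- Section 9.4 does not say who receives them. Sections 7.1, 7.6 and 9.5 exclude a monitoring board and an outside committee.
- Section 9.5 has the committee evaluating data once the assays have been run.
- It is therefore an inference, though the most natural one, that this committee receives the interim results.

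**Do the committee and the visit staff overlap?**

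- Section 9.5 makes up its committee from study personnel. Section 10.3.2 puts coordinators on the weekly quality control committee, and Section 10.2 has coordinators collecting participant data. Overlap is likely but not stated.
- Two further routes to assignments exist. Section 9.2 lets the PI, co-investigator, coordinators and clinic staff consult the schedule after a reaction, and Section 9.4 has study personnel carry out an unblinded safety review.

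**The case against.** A reader might infer that the trial is no longer double-blind for the remaining 360 participants. The documents do not support that. Knowing the assignments and results of a finished batch does not disclose anyone's rinse in the next one. Later participants still receive a coded, opaque syringe, and three sections state that the saliva collector is blinded. If Section 9.5 conflicts with those sections, the finding is an unreconciled contradiction and not proof that collectors are unmasked. The figure of 360 is a ceiling and does not measure bias.

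Other points on that side also carry weight:

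- Section 9.5 can be read as end-of-study interpretation, when unmasking is ordinary. That reading is possible, but the section sets no such limit and the interim has no other named reviewer.
- The committee in Section 10.3.2 reviews consent forms, data forms and adverse events. It is not described as reviewing assay results, and the section ends by denying that a quality control committee exists. It is supporting evidence only.
- Removal for low saliva volume follows set time points and a volume read from a marked tube. Samples carry only a random code, and assays are run in triplicate with controls. These limit bias in those steps. They do not cover the discretionary withdrawals, the change of assay or the dropping of arms.
- Coded tables cannot mask everyone. Staff who fill syringes must know the products and learn which one stops, so the fix has to allow for them.

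**Conclusion.** The concern holds in a limited form. Section 9.5 states a rule that contradicts the double-blind design and the blinding in Sections 5.2, 6.2.2, 6.2.3 and 9.2. It leaves the people who make several open-ended decisions free to know earlier assignments and results by arm.

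The exposure is up to 360 of 480 participants (75%) enrolled after the first review, and 60 to 300 if between one and five arms are dropped. This rests on two assumptions: that the committee in Section 9.5 receives the interim results, and that its members overlap with visit or laboratory staff. Both are likely, and neither is stated. The direction and size of any bias cannot be derived from the documents.

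This should be changed because the plan sets a harmful rule where a safer one costs little. It does not show that masking of individual participants fails.

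**What to change.** Replace the masking sentence in Section 9.5 with a rule to this effect: *The committee, visit staff and laboratory staff remain masked to assignment until every assay run has been accepted and the analysis is locked. The statistician presents interim and final tables by coded arm (A to F). The code is released only after the conclusions on coded arms have been recorded.*

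Section 9.4 should say that the statistician prepares the interim by coded arm, and who receives it. At the interim the team is told only which coded arms continue.

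List these exceptions explicitly:

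- emergency unblinding under Section 9.2
- the unblinded safety review under Section 9.4
- the staff who prepare syringes, who must know the products and any arm that stops, and who should not collect samples, run assays or judge outcomes

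Reconcile Sections 5.2, 6.2.2, 6.2.3, 9.2 and 10.3.2 with the new text, stating for each role who is masked and until when.

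The cost is mainly wording, since the statistician already creates the schedule. The downsides are small: existing roles must be separated, which may take some rearranging in one clinic, and the preparers will know which arm was dropped.
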